#### **4.5 Secondary MACE endpoints: Definition and Analysis**

The study has the below key secondary MACE endpoints which will be analyzed formally only if the primary analysis meets the noninferiority margin. A hierarchical testing scheme will be used to correct for the multiplicity of these endpoints. These endpoints are prioritized according to the following ordering:

- MACE plus hospitalization for HF or thromboembolic event excluding vascular access thrombosis
- Cardiovascular death, non-fatal MI or non-fatal stroke
- Cardiovascular death
- All cause death

## Statistical Analysis Plan MACE

For each of these secondary MACE endpoints, the hazard ratio (vadadustat/darbepoetin alfa) and its 95% confidence interval will be presented for each study and each pair of studies by the similar approach described for the primary MACE analysis. Kaplan-Meier or cumulative incidence curves will be generated too.

#### 4.6 Analyses of Secondary and Other Cardiovascular Safety Outcomes

The following table summarize the cardiovascular safety outcomes related to MACE, the associated definitions, and the model that will be applied to each outcome.

| Adjudicated Outcome  | Definition of Outcome
First bullet: time to event for subjects with a MACE
Second bullet: time to censoring for subject who do not experience a MACE   | Model   |
|--|---|---|
| Time to MACE within 4 weeks of End of Treatment                | 
 
• Date of the first MACE occurring within 4 weeks of EOT – date of first dose +1
 
• Date of last study visit (including telephone contact) within 4 weeks of EOT where all the components of MACE were assessed – date first dose +1
 
          | Cox regression model with same stratification factors and covariates as primary MACE analysis   |
| Individual CEC-adjudicated components of MACE                  | The frequency of each MACE component (all-cause mortality, nonfatal myocardial infarction, and nonfatal stroke) will be shown. For each subject, the total number of these outcomes (i.e., total number of MACE) will be calculated, and descriptive statistics for total number of MACE will be shown. | Not applicable  |
| Time to components of adjudicated MACE                         | 
 
• Date of the first MACE components – date of first dose +1
 
• Date of last study visit (included telephone contact) when where all the components of MACE were assessed – date of first dose +1
 
  | Cox regression model or competing risk analysis with same stratification factors and covariates as primary MACE analysis                                      |
| Time to expanded MACE  | 
 
• Date of the first MACE (expanded definition) – date of first dose +1
 
• Date of last study visit (included telephone contact) when where all the components of MACE (expanded definition) were assessed – date of first dose +1
 
             | Cox regression model with same stratification factors and covariates as primary MACE analysis   |
| Time to Cardiovascular death, non-fatal MI or non-fatal stroke | 
 
• Date of first MACE – date of first dose +1
 
• Subject’s date of last contact – date of first dose +1
 
  | Competing risk analysis with same stratification factors and covariates as primary MACE analysis. Non-cardiovascular and unknown deaths are competing events. |
| All-cause death  | 
 
• Date of death – date of first dose +1
 
• Subject’s date of last contact – date of first dose +1
 
   | Cox regression model with same stratification factors and covariates as primary MACE analysis   |

## Statistical Analysis Plan MACE

| Adjudicated Outcome                             | Definition of Outcome
First bullet: time to event for subjects with a MACE
Second bullet: time to censoring for subject who do not experience a MACE   | Model   |
|---|---|---|
| Cardiovascular death                            | 
 
• Date of cardiovascular death – date of first dose +1
 
• Subject’s date of last contact – date of first dose +1
 
  | Competing risk analysis with same stratification factors and covariates as primary MACE analysis. Non-cardiovascular and unknown deaths are competing events. |
| Non-cardiovascular death                        | 
 
• Date of non-cardiovascular death – date of first dose +1
 
• Subject’s date of last contact – date of first dose +1
 
  | Competing risk analysis with same stratification factors and covariates as primary MACE analysis. Cardiovascular and unknown deaths are competing events.     |
| Time to any thromboembolic event                | 
 
• Date of first occurrence of adjudicated arterial thrombosis, DVT, PE, or vascular access thrombosis – date of first dose +1
 
• Date of last study visit (including telephone contact) where such events were assessed – date of first dose +1
 
 | Competing risk analysis with same stratification factors and covariates as primary MACE analysis. All –cause death is a competing event.                      |
| Time to arterial thrombosis, DVT, or PE         | 
 
• Date of first occurrence of adjudicated arterial thrombosis, DVT, or PE thrombosis – date of first dose +1
 
• Date of last study visit (including telephone contact) where such events were assessed – date of first dose +1
 
                  |   |
| Time to venous thromboembolic event (DVT or PE) | 
 
• Date of first occurrence of adjudicated DVT or PE – date of first dose +1
 
• Date of last study visit (including telephone contact) where such events were assessed – date of first dose + 1
 
  |   |
| Hospitalization for heart failure               | 
 
• Date of first occurrence of adjudicated hospitalization for heart failure – date of first dose +1
 
• Date of last study visit (including telephone contact) where such events were assessed – date of first dose + 1
 
                          |   |

The following outcomes will be summarized as proportions and are purely descriptive as they do preserve the randomized groups. That is, only subjects with CEC-confirmed MI or strokes are included in these calculations, respectively.

|                        |   |
|------------------------|---|
| 30-day MI fatality     | The proportion is calculated as the number of deaths occurring within 30 days of an CEC-confirmed MI divided by the number of subjects who had an CEC-confirmed MI. |
| 30-day stroke fatality | The proportion is calculated as the number of deaths occurring within 30 days of an CEC-confirmed MI divided by the number of subjects who had an CEC-confirmed MI. |

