#### **3.1 Adjudicated Outcomes**

Study investigators will solicit potential cardiovascular events at each study visit. Each of these potential events will be recorded on the eCRF. Potential cardiovascular events will also be identified through periodic review of Standard MedDRA Queries (SMQs) of adverse events and serious adverse events irrespective of the source of identification. An Endpoint Management Plan will provide details describing the SMQs terms and processes related to identifying these potential events. Events not reported by study investigators identified through SMQ search or CEC will be manually entered into EAS (Endpoint Adjudication System) database.

The Clinical Endpoint Committee (CEC) adjudicates all potential cardiovascular events. The formal cardiovascular safety analyses will only include CEC-adjudicated events (i.e., events confirmed by the CEC).

The CEC adjudicates the following events CEC Manual of Operations (MOP) outlines the program endpoint definitions and requirements for committee adjudication.

- All-cause mortality (The CEC will attribute cause of death to responsible underlying disease cause).
- Non-cardiovascular death
- Unknown death
- Cardiovascular death
  - Sudden death
  - Non-sudden cardiovascular death

- Fatal or nonfatal MI
- Fatal or nonfatal stroke
- Thromboembolic event
  - Arterial thrombosis
  - Deep vein thrombosis (DVT)
  - Pulmonary embolism (PE)
  - Vascular access thrombosis
- Hospitalization for heart failure (HF)

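### MACE SAP 4.6 defines 30-day stroke fatality with MI in both numerator and denominator, so the stroke row would repeat the MI row

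*SAP*

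**What the plan says.** After the table of cardiovascular outcomes in section 4.6, the MACE SAP adds a short second table of two proportions. Its lead-in sets their status: "The following outcomes will be summarized as proportions and are purely descriptive". The reason offered is that they are "purely descriptive as they do preserve the randomized groups". It then states who is counted: "only subjects with CEC-confirmed MI or strokes are included in these calculations, respectively".

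Two rows follow, labelled "30-day MI fatality" and "30-day stroke fatality". The definition in each row is a count of "deaths occurring within 30 days of an CEC-confirmed MI divided by the number of subjects who had an CEC-confirmed MI". The text of the two definitions is the same word for word.

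**The concern.** The stroke row looks like a copy of the MI row in which the event name was not changed. An analyst who follows the definition would report MI case fatality under a stroke label and would never compute stroke case fatality.

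The lead-in compounds this. A proportion taken only among subjects who went on to have an MI or a stroke is conditional on something that treatment may influence. The two arms' subsets are therefore no longer the randomized groups. That is the reason to keep the result descriptive, yet the sentence asserts the opposite.

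Stroke is not a peripheral outcome in this programme. The SAP's own justification of the MACE margin (headed Appendix B, with sections numbered C) singles out stroke as the component that caused concern when ESAs were used to reach higher hemoglobin. It cites a hazard ratio of 1.923 (95% CI 1.379 to 2.681). A wrong stroke safety output would be awkward to explain after unblinding, particularly in open-label trials.

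**Working it through.** No arithmetic in the plan needs reproducing. The check compares texts.

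**1. The two rows side by side (MACE SAP 4.6)**

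| | MI row | Stroke row |
|---|---|---|
| Numerator as written | deaths within 30 days of a confirmed MI | deaths within 30 days of a confirmed MI |
| Denominator as written | subjects with a confirmed MI | subjects with a confirmed MI |
| Implied by label and lead-in | MI in both | stroke in both |

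**2. What literal programming gives.** Let D_MI be deaths within 30 days of a confirmed MI and N_MI the subjects with a confirmed MI, and define D_S and N_S in the same way for stroke.

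- MI row as written: D_MI / N_MI
- Stroke row as written: D_MI / N_MI
- Difference between the rows: D_MI / N_MI − D_MI / N_MI = 0, in each arm and each study, whatever the data
- Intended stroke row: D_S / N_S, which is never formed

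**3. Whether the intent is in doubt.** It is not. The label names stroke, and the lead-in assigns MI subjects to one row and stroke subjects to the other. The definition is the only element that disagrees.

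**4. Whether another place supplies the right definition.** Section 3.2.4 lists fatal stroke and non-fatal stroke as time-to-first-event components, which is a different quantity from 30-day deaths over subjects with a stroke. Appendix A holds code only for competing risks and restricted mean survival time. The general SAP and the protocol do not define a 30-day stroke fatality.

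**5. Whether the correct quantity can be computed.** It can. Section 3.1 has the CEC adjudicating "Fatal or nonfatal stroke", and all deaths are collected.

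**6. The lead-in.** Its second sentence restricts each calculation to subjects who had the event. That restriction is made after randomization, so the first sentence is coherent only with a negative before the verb.

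**7. Whether this is an artefact of the file.** Both rows are complete, well-formed sentences, with no gap or redaction.

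**The case against.** The best reply is that this is a typing error with almost no reach. A programmer who reads the label and the lead-in would see what was meant, and the SAP's introduction provides for a blinded team to review the data and settle conventions. The outcome is descriptive. It sits outside the primary MACE analysis (section 4.4) and outside the hierarchical secondary endpoints (section 4.5), so no margin, alpha or decision rule moves. The stroke signal behind the quoted hazard ratio concerns whether strokes occur, not whether patients die soon after one. That question is answered elsewhere, by the time-to-event analyses of fatal and non-fatal stroke. The missing negative in the lead-in changes no calculation, because the plan already treats the proportions as descriptive.

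All of this stands as a limit on importance. In particular, the hazard ratio of 1.923 shows why stroke outputs will be read closely; it does not show that stroke safety goes unexamined. None of it makes the printed definition right. The same introduction says that the document's language and code specify the intent of each analysis. A definition that has to be overridden from its label does not do that.

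**Conclusion.** The concern holds. As written, the stroke row is wrong in both numerator and denominator and duplicates the MI row. The lead-in states the reverse of the reason it needs.

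The size is one descriptive row, wrong in full if programmed literally. Because the MACE SAP serves both the PRO₂TECT and INNO₂VATE pairs, the error would recur across four trials. It has no effect on the noninferiority conclusion for MACE, on the ordered secondary endpoints or on any power figure.

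The conclusion assumes that the row is programmed from its definition and not from its label, and that no unseen table shell or programming specification corrects it. If one does, the SAP text should still be brought into line. This should be corrected, but it does not threaten the trial's main results.

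**What to change.** In section 4.6 of the MACE SAP:

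- Define the stroke row as the number of deaths within 30 days of a CEC-confirmed stroke, divided by the number of subjects who had a CEC-confirmed stroke.
- In the lead-in, insert *not*, so that the sentence says the proportions do not preserve the randomized groups.

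The cost is two word replacements in the definition and one inserted word in the lead-in. No new data, analysis or sample size is involved. Make the change before database lock and unblinding, and check that any table shells and programming specifications carry the corrected definition.

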## 5 SUBGROUPS

The effects of vadadustat compared to darbepoetin alfa on the incidence of the primary safety outcome will be examined across the following subgroups. All subgroup analyses are regarded as exploratory.

### 5.1 Prespecified Subgroups

The main MACE analysis will be presented separately within the following subgroups. In each case, if the subgroup is a stratification factor or a covariate (indicated in italics), the model will be the same as the overall model with the deletion of the respective stratification factor or covariate. Subgroup analyses will be performed only if the total number of outcomes in a stratum, combined over the two treatment groups, is at least 100.

#### *Randomization stratification factors*

- Hb stratification level at baseline
  - PRO2TECT
    - Low level group (<9.5 g/dL for CI-0014; <10.0 g/dL for CI-0015)
    - High level group (≥9.5 g/dL for CI-0014; ≥10.0 g/dL for CI-0015)
  - INNO2VATE
    - Low level group (<9.5 g/dL for CI-0016; <10.0 g/dL for CI-0017)
    - High level group (≥9.5 g/dL for CI-0016; ≥10.0 g/dL for CI-0017)
- Region
  - US
  - EU
  - ROW
- NYHA CHF stratification level
  - 0 and 1

- 2 and 3
- Target Hb level: These targets are completely confounded with region. The 10-11 g/dL target consists of subjects from the US while the 10-12 g/dL target applies to the EU and the ROW.
  - 10-11 g/dL
  - 10-12 g/dL

*Demographics and medical history*

- Age
  - <65 years
  - ≥65 years
- Sex
  - Male
  - Female
- Ethnicity
  - Hispanic
  - Non-Hispanic
- Race
  - White
  - All others
- Diabetes mellitus
  - No diabetes mellitus
  - Diabetes mellitus
- History of cardiovascular disease (defined as medical history of coronary artery disease, myocardial infarction, stroke, or heart failure as captured by four separate questions on the Case Report Form)
  - Yes
  - No
- For CI-0016 and CI-0017 only, type of dialysis

- Hemodialysis
- Peritoneal dialysis

*Medications (CI-0015 and CI-0017 only)*

- Baseline ESA dose (See Locatelli, 2004 for justification of the choice of cut-off values)
  - <90 U/kg/week
  - ≥90 U kg/week
  - >300 U/kg/week

*Baseline laboratory measurements*

- For CI-0014 and CI-0015 only, urine albumin creatinine ratio (uACR) (See Gansevoort, 2011 for a justification of the choice of cut-off values)
  - <300 mg/g
  - ≥300 mg/g
- For CI-0014 and CI-0015 only, estimated GFR (The threshold of 15 represents a value between CKD eGFR Categories 4 and 5)
  - <15 ml/min/1.73m^2 (CKD Stage 5)
  - ≥ 15 ml/min/1.73m^2 (CKD stage 4 or lower)
- C-reactive protein. In Q2 laboratories, which are the laboratories used in these studies, the normal range is 0-0.6mg/dL.
  - ≤0.6 mg/dL
  - >0.6 mg/dL
- Baseline transferrin saturation (TSAT)
  - CI-0014 and CI-0015
    - < median of CI-0014 and CI-0015 combined
    - ≥ median of CI-0014 and CI-0015 combined
  - CI-0016 and CI-0017
    - < median of CI-0016 and CI-0017 combined
    - ≥ median of CI-0016 and CI-0016 combined
- Baseline ferritin

- CI-0014 and CI-0015
  - < median of CI-0014 and CI-0015 combined
  - $\geq$  median of CI-0014 and CI-0015 combined
- CI-0016 and CI-0017
  - < median of CI-0016 and CI-0017 combined
  - $\geq$  median of CI-0016 and CI-0017 combined
- Incident Dialysis Patients
  - CI-0016 and CI-0017
    - All patients in CI-0016 plus patients who have  $\leq 16$  weeks of dialysis history from the date of informed consent in CI-0017
- Pooled analysis of patients with CKD G5 and incident dialysis patients (those who initiated dialysis within 16 weeks) after all studies indicated below are completed
  - <15 ml/min/1.73m^2 (CKD Stage 5) at baseline from CI-0014 and CI-0015
  - All patients in CI-0016 plus patients who have  $\leq 16$  weeks of dialysis history from the date of informed consent in CI-0017

In these summary statistics, only the primary analysis method will be presented. Hazard ratios and their 95% confidence intervals for subgroups will be displayed using forest plots.

## 5.2 Subgroup Analyses of Other Outcomes

Exploratory post-hoc analyses of other outcomes may be performed to gain insight into the effect of the drugs in other subgroups.

## 6 SUPPORTIVE ANALYSIS - RESTRICTED MEAN SURVIVAL TIME

Recent papers on time to event, especially regarding trials assessing cardiovascular safety of non-cardiovascular drugs [e.g., Uno, 2015, Zhao, 2016] have recommended use of the restricted mean survival time (RMST), rather than hazard ratio, to assess the effect of drugs. As a supportive analysis, we will compare the RMST in the two treatment arms for the PRO2TECT and INNO2VATE pairs of studies for the primary MACE event.

To specify RMST, one needs to select a time T. An event that occurs prior to time T “counts” in the analysis; events that occur after T do not enter the analysis. T will be selected as the 75th percentile of follow-up time.

## 7 DATA SAFETY MONITORING

An independent statistical analysis center performs analyses in support of the IDMC which meets approximately every 4 to 6 months throughout the course of the study.

The IDMC and the independent statistician will be the only people who will be unblinded to these MACE data.

The IDMC will also consider early termination if the quality of trial conduct is such that the trial will not be able to provide a timely and reliable answer to the questions it was designed to address.

## 8 HANDLING OF MISSING DATES

For all adjudicated events, the CEC-determined date of the event will be used in all analyses. In the unlikely event that this date is missing then the investigator-reported date will be used.

For an incomplete date of an endpoint event, imputation will be performed as outlined below:

- If the event date is completely missing, date is set to date of first dose.
- If year is present and month and day are missing or year and day are present and month is missing:
  - If year = year of first dose, then set month and day to month and day of first dose.
  - If year < year of first dose, then set month and day to December 31.
  - If year > year of first dose, then set month and day to January 1.
- If month and year are present and day is missing:
  - If year = year of first dose and
    - month = month of first dose, then set day to day of first dose date.
    - month < month of first dose, then set day to last day of month.
    - month > month of first dose, then set day to first day of month.
  - If year < year of first dose, then set day to last day of month.
  - If year > year of first dose, then set day to first day of month.
- For all other cases, set date to date of first dose.

If the above imputations produce an illogical date, a logical date will be selected by a statistical team blinded to everything but the dates.

For an incomplete death date, imputation will be performed using the same rule as described above.

## 9 SUBJECT DISPOSITION, TREATMENT ADHERENCE, AND TREATMENT EXPOSURE

The main SAPs for PRO2TECT and INNO2VATE summarize methods for describing subject disposition, adherence to treatment, and exposure to treatment.

**APPENDIX A. SAS CODE**

This below SAS codes are for competing risk analysis and restricted mean survival time analysis.

**Competing Risk**

```
proc phreg data=&INDAT.;  
  class study TRT(ref="DARB") STRAT2_HF STRAT3_REG AGE SEX  
    RACE HX_CV_ALL HX_DM;  
  strata study;  
  model T*Status(0)= HB_base STRAT2_HF STRAT3_REG TRT AGE SEX RACE  
HX_CV_ALL HX_DM / eventcode=1 ties=Efron rl;  
  Ods ouput ParameterEstimates = HR_EST;  
Run;
```

**Restricted Mean Survival Time (RMST)**

```
proc lifetest data=&INDAT. plots=(rmst) rmst(tau=&fut);  
  time SurvTime*Censor(1);  
  strata study /group=TRT;  
run;
```

where &fut is the 75th percentile of follow-up time.

## **APPENDIX B. JUSTIFICATION OF THE NONINFERIORITY MARGIN**

This appendix provides the rationale for the noninferiority margin of 1.25 in MACE analysis for FDA decision making and for the noninferiority margin of 1.30 for EMA decision making.

### **C.1. Background**

Many scientific questions are unanswered to date and there remains an unmet medical need for a new therapy for anemia in CKD. Among the unanswered questions are:

- Can Hgb be safely raised with a novel agent other than an ESA without increasing CV risk?
- Are hypoxia-inducible factor prolyl-hydroxylase inhibitors (HIF-PHIs) as safe as or safer than ESAs?

The primary safety outcome in each study is MACE, defined as all-cause mortality, nonfatal myocardial infarction (MI) or nonfatal stroke, occurring at any time following randomization and prior to each subject's end-of-study date. The endpoint for the primary analysis will be the first occurrence after randomization of all-cause mortality, adjudicated nonfatal MI, or adjudicated nonfatal stroke. Treatment comparisons will be based on the estimated hazard ratio (vadadustat/darbepoetin alfa) and its 95% CI from a Cox proportional hazards model for the pair of NDD studies and for the pair of DD studies.

Vadadustat will be considered to have non-inferior risk of MACE relative to darbepoetin alfa if the upper limit of this 95% CI of each pair of studies is less than or equal to the prespecified noninferiority margin.

### **C.2. FDA Decision Making**

#### **C.2.1. Feasibility of and MACE Event Rates in Trials of Subjects with Anemia Secondary to CKD**

While the number of adults diagnosed with CKD in the US is 3.9 million (CDC 2015), the number of individuals with anemia and NDD-CKD is significantly lower. According to recent claims data, 10% of NDD-CKD stage 3 patients and 20% of NDD-CKD stage 4 patients have Hgb<10 g/dL (Thamer 2014). Moreover, the number of patients being treated for anemia continues to decline. This is consistent with recent claims data demonstrating that 11% of NDD-CKD stage 3 patients and 27% of NDD-CKD stage 4 patients are being treated with an ESA (Thamer 2014). This low utilization of ESA reflects changes in practice patterns as a result of TREAT (Pfeffer 2009) as well as the change in the ESA labels in the US. As a result, the impact on the feasibility of successfully executing a clinical trial of anemia in CKD must be considered with these changing practices. In fact, recent trials have taken longer to execute than did trials in the past. For example, the CHOIR (Singh 2006) and PEARL (Macdougall 2013) trials had broad inclusion/exclusion (I/E) criteria (e.g., Hgb<11.0 g/dL) and were able to recruit patients at a rate of 0.30-0.40 patients per site per month (p/s/m). In contrast, more recent trials requiring Hgb inclusion of <10.0 g/dL have had recruitment rates of 0.10-0.15 p/s/m (ClinicalTrials.gov NCT00922587 and NCT01887600). Put into practical terms, a trial needing 2000 CKD patients with Hgb<10.0 g/dL and recruiting at a rate of 0.10 p/s/m would require nearly 850 sites to recruit over 24 months. This is impractical given the limited number of nephrology

investigators; utilizing so many sites risks making a trial unfeasible. As a consequence, future trials require an extended timeline for recruitment, leading to a delay in the availability of new therapies for patients with CKD. In addition, these delays limit the potential clinical applicability as patient populations and practice patterns evolve.

Of the nearly 500,000 patients with dialysis-dependent CKD (DD-CKD) in the US, more than 80% require therapy for anemia and would potentially qualify for inclusion into a trial. However, addition of specific I/E criteria, competition with other trials, and the limited number of nephrology research centers available to perform research again negatively impact execution of DD-CKD trials. For example, for an incident dialysis trial where only 0 or 1 new patient starts dialysis per month in a given research center, anticipated recruitment rate is <0.20 p/s/m. Thus, a trial requiring enrollment of 400 patients would need at least 80 sites enrolling for over 24 months, not including time for start-up.

In addition to the aforementioned considerations, the event rate must also be factored into the feasibility of a trial. In development of our trials, while we have assumed a 10% annualized MACE event rate in NDD-CKD and 12% in DD-CKD, we understand that this event rate may decrease over time with improved medical care. Our event rates are based on review of contemporary population level data (USRDS), recent CKD trials (BEACON [de Zeeuw 2013]), and anemia in CKD trials. For NDD-CKD, given the narrower inclusion criteria of Hgb<10 g/dL, we assumed most patients would have later stage CKD with MACE event rates similar to that in TREAT at 10% overall. For MACE in DD-CKD, we reviewed the event rates from contemporary population-level data (USRDS), recent ESRD trials, EVOLVE (Chertow 2012), AURORA (Fellstrom 2009), and anemia in ESRD trials EMERALD (Fishbane 2013) and NHT (Besarab 1998). Only EMERALD and EVOLVE had applicable information on MACE event rate. While EMERALD had a MACE event rate of ~14.5%, EVOLVE had an 11.5% rate and thus 12% was conservatively selected. While Akebia considered enrichment to reduce the overall sample size knowing the difficulty we may have enrolling these trials, the feasibility trade-offs ruled out this option. For example, RED-HF (Swedberg 2013), an anemia trial in patients with heart failure, recruited at <0.10 p/s/m and had to extend enrollment to nearly 6 years. Rather than enrich the Akebia trials, we have assumed moderate event rates with the knowledge that the trials may need to be extended if the event rates decrease over time. For example, if an annual event rate of 8% is observed rather than our estimated 10%, the NDD-CKD studies will need to be extended by approximately 6 months given our baseline assumptions.

Taken together, we have considered the prevalence of anemia in CKD, narrower I/E criteria, and lower event rates over time when determining a reasonable trial design and sample size for our development program.

